6. ANALYSES AND SUMMARIES

Data will be summarized by dose group, regimen group and the subgroup of subjects who are initially assigned to tofacitinib 5 mg BID and later are retreated with tofacitinib 10 mg BID.

Efficacy analyses will be based on FAS and safety analyses will be based on the safety analysis set. Demographics and baseline characteristics will be summarized for the FAS.

6.1. Primary Efficacy Endpoint

The primary efficacy endpoint is remission based on modified Mayo score at Month 6.

As detailed in [Section 5.2.1](#), the number and proportion of responders will be presented by dose group. The stratified estimation of the treatment difference between dose groups will be presented along with its 95% CI.

6.2. Secondary Efficacy Endpoints

Time to loss of remission (flare) based on modified Mayo score will be analyzed as described in [Section 5.2.4](#).

Binary secondary efficacy endpoints will be analyzed using the same approach as described for the primary efficacy endpoint.

Change from baseline (of Study A3921288) in modified Mayo score, modified partial Mayo score, total Mayo score, and partial Mayo score will be analyzed as described in [Section 5.2.2](#).

Fecal calprotectin and hs-CRP, and their change from baseline will be summarized descriptively for each visit by dose group and by regimen group.

The fecal calprotectin and hs-CRP data will also be log-transformed (natural logarithm) for the analyses. The change from baseline will be analyzed using the same approach as the continuous efficacy.

CCI

6.4. Subset Analyses

Subgroup analyses will be conducted for remission based on modified Mayo score, remission based on total Mayo score, remission based on partial mayo score and MH for Endoscopic subscore at baseline (0, 1), prior TNF failure (Y/N), prior TNF exposure (Y/N). The number and proportion of responders will be presented by dose group, regimen group in each

subgroup. The difference between groups will be presented along with its 95% confidence interval using the normal approximation for the difference in binomial proportions. P-value based on the Chi-square test will be used to test for the group difference within a subgroup unless the cell frequencies are too small. In this case, the Fisher's exact test will be used.

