Based on the Phase 3 data, the observed treatment effect was higher with tofacitinib 10 mg BID than tofacitinib 5 mg BID maintenance therapy and a dose-dependent response observed in the rate of herpes zoster. While the data from the uncontrolled open-label LTE study suggest maintenance of efficacy with dose reduction to 5 mg BID for subjects who are in remission after 52 weeks of receiving tofacitinib 10 mg BID, this double-blind, randomized study may help to further evaluate the benefits of dosing flexibility with tofacitinib, and provide additional data for selecting the most appropriate regimen for an individual subject.

This study is designed to evaluate (1) the efficacy and safety of tofacitinib in subjects in stable remission on 10 mg BID who decrease the dose to 5 mg BID compared to subjects remaining on 10 mg BID; (2) the efficacy and safety of tofacitinib in subjects in stable remission on 10 mg BID who decrease the dose to 5 mg BID with option for dose escalation for flare ("flexible dosing regimen") compared to subjects staying on 10 mg BID; and (3) the efficacy and safety of the subset of subjects who have flare on maintenance tofacitinib 5 mg BID and are re-treated with 10 mg BID.

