4.3. Randomization Criteria

Eligible subjects will be randomized in a 1:1 allocation ratio to receive either tofacitinib 5 mg BID or 10 mg BID at baseline of Study A3921288. Subjects will be stratified at baseline based on the endoscopic subscore (0 versus 1) of their most recent endoscopy.

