9.1. Sample Size Determination

Although approximately 130 subjects are estimated to be enrolled into this study (based on availability of eligible subjects from the open label Study A3921139 and based on the conservative assumptions of the attrition rate of 50% - 50% in Study A3921139), the final sample size may exceed 130 subjects. The Sponsor will continue to engage with investigative sites participating in Study A3921139 to assess the ability to enroll additional eligible subjects.

With 130 (65 per group) subjects, the estimated half width of the 95% confidence for treatment difference between tofacitinib 10 mg BID and 5 mg BID in proportion of remission at Month 6 based on the modified Mayo score is about 16%, assuming the remission rates are greater than 70% in both groups.

At the time of Amendment 2, 138 subjects have been enrolled and approximately 122 subjects have crossed their Month 6 study visit, the timepoint of the primary endpoint.

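### The SAP's subgroup section plans no comparison of the dose effect between subgroup levels, and its normal-approximation intervals would be unreliable if remission in a small level came close to 100%

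*SAP*

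**What the plan says.** SAP 6.4 covers four binary endpoints: remission by modified Mayo, total Mayo and partial Mayo score, and mucosal healing. The factors are baseline endoscopic subscore (0, 1), prior TNF failure and prior TNF exposure. In each level the plan reports counts and proportions by dose group and by regimen group, and the difference with its "95% confidence interval using the normal approximation for the difference in binomial proportions". It then states: "P-value based on the Chi-square test will be used to test for the group difference within a subgroup". The same sentence excepts cells that are too small, for which Fisher's exact test is used. No cut-off for too small is given.

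Three other places bear on this:

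- SAP 5.2.1 uses the stratified Newcombe interval for the main binary analyses.
- SAP 6.6.1 uses the normal approximation for tier-2 adverse events, but withholds the interval when a group has no events. Section 6.4 has no corresponding rule for 0% or 100%.
- SAP 5.1 states that there are no formal hypotheses to test.

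The only interaction terms in either document are dose or regimen group by visit (SAP 5.2.1 and 5.2.2; Protocol 9.2.3 and 9.3). None involves a subgroup factor.

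**The concern.** Whether a dose effect differs between two groups of patients is a question about the difference between two differences. Two separate p-values do not address it. In levels of modest size and power, one will often fall below 0.05 and the other not, even when the effect is identical. Readers commonly take that pattern as a subgroup effect. Protocol 1.2 says that the trial may "provide additional data for selecting the most appropriate regimen for an individual subject", so some readers will turn to the subgroup tables for that purpose.

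The second issue is the interval. The plan leaves Newcombe for the normal approximation in the analyses with the fewest subjects. Every subject enters in remission, so a small level could have an observed rate at or near 100%, where the normal approximation gives intervals that are too short or have no width.

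**Working it through.** **Inputs from the documents.** Protocol 9.1: "With 130 (65 per group) subjects", half-width "is about 16%, assuming the remission rates are greater than 70% in both groups"; at Amendment 2, "138 subjects have been enrolled and approximately 122 subjects have crossed their Month 6 study visit". Protocol 4.3: 1:1 allocation. Protocol 1.2: 72.7% in remission and 81.8% with mucosal healing after 12 months in the uncontrolled extension study. These last two are different endpoints in one group, and are used together here only as an illustrative pair.

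**Assumed.** The documents give no subgroup sizes or subgroup rates. I take 20 or 35 per arm per level as the base cases (two levels of 35 make 70 per arm, close to 138/2 = 69). Further splits of 65 per arm run from 33/32 to 50/15. Rates range from the documents' values up to 98%.

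**1. The plan's own figure.** 1.96 × √(2 × 0.70 × 0.30 / 65) = 0.1575, or 15.8 points. This reproduces the stated 16%.

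**2. One level significant, the other not, under an identical true effect.** If the power in the two levels is π_A and π_B, the chance is π_A(1 − π_B) + π_B(1 − π_A). Power is by exact binomial enumeration of the chi-square test.

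- 90% vs 75%, 35 per arm in each level: π = 0.383, so 2 × 0.383 × 0.617 = 0.47. Using Fisher when an expected count is below 5 (my cut-off) gives 0.46.
- 81.8% vs 72.7%, 35 per arm: π = 0.142, so 2 × 0.142 × 0.858 = 0.24. With 20 per arm in each level it is 0.19.
- Splits of 65 per arm from 33/32 to 50/15, with the Fisher fallback: 0.43 to 0.52 at 90% vs 75%, and 0.22 to 0.24 at 81.8% vs 72.7%.

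**3. Coverage of the nominal 95% interval**, by exact enumeration. The chance that both arms are at 100%, which gives zero width, is p₁ⁿ × p₂ⁿ.

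| True rates | n per arm | Normal approximation | Newcombe | Both arms at 100% |
|---|---|---|---|---|
| 81.8% vs 72.7% | 20 | 93.1% | 95.8% | about 0 |
| 81.8% vs 72.7% | 35 | 94.1% | 95.1% | about 0 |
| 97% vs 90% | 20 | 87.1% | 99.1% | 6.6% |
| 97% vs 90% | 35 | 93.7% | 98.3% | 0.9% |
| 98% vs 95% | 20 | 75.6% | 99.8% | 23.9% |
| 98% vs 95% | 35 | 83.0% | 99.1% | 8.2% |

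For example, 0.98²⁰ × 0.95²⁰ = 0.668 × 0.358 = 0.239. With equal high rates (95% in both arms, n = 20) the normal approximation does not under-cover (98.8%). The failure there is the zero-width interval, in 12.9% of trials.

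At 20/20 vs 20/20 the normal approximation gives [0, 0] and Newcombe gives −16.1 to +16.1 points.

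**4. Precision of the missing contrast.** The half-width is 1.96 × √(v/n_a + v/n_b), where v = p₁(1 − p₁) + p₂(1 − p₂) and n_a, n_b are the numbers per arm in the two levels.

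- 70% in all cells, v = 0.42: 31.5 points (33/32) to 34.1 points (45/20), against 15.8 for the overall difference.
- 90% vs 75%, v = 0.2775: 25.6 to 27.7 points, against 12.8 overall.

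**The case against.** Four points on the other side have force.

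- A reader might infer from Protocol 1.2 that effect modification is the trial's own question. It is not. The objectives are the dose comparison, the regimen comparison and a description of re-treated subjects. The sentence in 1.2 concerns dosing flexibility and names no subgroup factor.
- A reader might also infer that the planned output cannot show whether the effect differs. That holds for the p-values alone. The two levels of a factor contain different subjects, and each has a difference with an interval. Standard errors, and so the contrast, can be back-calculated, except that a zero-width interval gives no usable standard error. What is missing is a planned and displayed estimate.
- The SAP nowhere says that it will infer a subgroup effect from one significant and one non-significant level. It reports differences with intervals beside the p-values, tests no formal hypotheses, and has a Fisher fallback for small cells.
- The documents give no rates near 100%. At 81.8% vs 72.7% the normal approximation is short by only one to two points of coverage. Counting missing and escalated subjects as non-responders lowers rates further.

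All four stand, and they limit the point to interpretation. They do not remove it. The absence of formal hypotheses argues against within-level p-values rather than for them, the Fisher fallback leaves the interval unchanged, and [0, 0] at 100% in both arms is a wrong interval under the rule as written.

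**Conclusion.** The point holds as a minor one, confined to how exploratory subgroup results are read. The primary and main secondary binary analyses use the stratified Newcombe interval and are unaffected.

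The gap in the plan is certain: no between-level contrast is specified, and 6.4 has no rule for 0% or 100%. Its consequences depend on assumed sizes and rates. With 35 per arm in each level, a uniform dose effect would give a significant result in exactly one level in about a quarter (81.8% vs 72.7%) to about a half (90% vs 75%) of trials.

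A claim that the intervals in 6.4 are generally invalid would go too far. They are adequate at rates like those in the documents and fail only if rates in small levels approach 100%. That is plausible because all subjects enter in remission, but it is not documented.

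**What to change.** In SAP 6.4, for both the dose-group and the regimen-group comparisons:

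1. Replace the normal-approximation interval with the unstratified Newcombe interval, in line with 5.2.1.
2. For each factor, add one difference of risk differences between the two levels with a 95% CI, labelled exploratory. Building it from the within-level Newcombe limits would keep it from collapsing at 100%.
3. Drop the within-level p-values, or label them descriptive and state that a difference in significance between levels is not evidence of a subgroup effect.

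The cost is a few lines of SAP text and a small programming change. No data collection and no primary analysis changes. There are two drawbacks. Newcombe is conservative near 100% (98.3% to 99.8% coverage in the high-rate rows of the table). The contrast will be wide, about ±26 to ±34 points under the assumed sizes and rates, so it will mostly show how little the subgroups can say.

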6.5. Baseline and Other Summaries and Analyses

6.5.1. Baseline Summaries

Demographics and baseline characteristics will be summarized by dose group based on FAS.

6.5.2. Study Treatment Exposure

Subjects were expected to take 4 tablets per day (2 tablets on a BID schedule) during the double-blind treatment period. However, since the number of tablets taken could be for a full day or only for a half day on the first treatment date or last treatment date, for simplicity, we assume that the first treatment date and last treatment date are days that the subjects took the expected number of tablets. The study drug compliance is defined as:

Drug compliance = (Actual Number of Tablets taken / Expected number of tablets)*100%.

Where expected number of tablets is defined as (Treatment Duration – 2)*expected number of tablets per day+ the actual number of tablets taken on the first and the last treatment dates if treatment duration >=2 days. If a subject only took drug on the first day, we assumed he/she took the expected number of tablets on that day, and define the compliance=100%.

Treatment duration in days is calculated as last treatment date – first treatment date +1.

6.6. Safety Summaries and Analyses

The safety data will be summarized in accordance with Pfizer Data Standards.

All safety data will be summarized descriptively by dose group, regimen group and the subgroup of subjects who are initially assigned to tofacitinib 5 mg BID and later are retreated with tofacitinib 10 mg BID in the safety analysis set.

6.6.1. Adverse Events

The analyses of adverse events under the 3-tier approach described in [Section 3.5](#) is considered exploratory. There will be no adjustment for multiple comparisons or stratification factors in the analyses. For tier-1 events, the proportion of AEs observed in each group will be presented along with the point estimates and associated 95% confidence intervals of the risk difference, and p-value for dose comparison or regimen comparison using the exact methods proposed by Chan and Zhang (1999)² described in [Section 5.2.5](#). For tier-2 events, the proportion of AEs observed in each group will be presented along with the point estimates and associated 95% confidence intervals of the risk difference using the normal approximation for the difference in binomial proportions. In case of zero event rate for tier-2 events in any of group, the 95% confidence intervals will not be computed. AEs will be arranged in the output sorted in descending point estimate of the risk difference within system organ class. Tier 3 AEs will not be summarized separately, they are included

in the overall standard AE summary. Footnotes in the outputs will include the methods used to derive any p-values and confidence intervals as per Pfizer standards.

A listing of subjects with dose reduction due to PE risk factors will be provided.

Incidence Rates (IR) of Adverse Events of Special Interest will be provided. Confidence intervals (95%) will be computed using the exact Poisson method.

For regimen groups, IR will be calculated only for adverse event data for events of special interest only. The numerator will be the number of unique subjects with a treatment emergent event as defined above during the interval from the first dose in A3921288 study to last dose of tofacitinib + 28 days at risk period. The denominator of the incidence rate is person time accruing from the subject's first dose to last dose + 28 days, or to the date of the first event, whichever occurs earlier. For a subject who died, the time will be the minimum of (the date of the last dose + 28 days, or death date).

For dose groups, IR will be calculated only for adverse events of special interest only. The numerator will be the number of unique subjects with a treatment emergent event as defined above during the interval from the first dose in A3921288 study to dose adjustment for dose escalated or dose reduced subjects otherwise to last dose + 28 days at risk period. The denominator of the incidence rate is person time accruing from the subject's first dose to day of dose escalation, or the first dose to day of dose reduction, or last dose + 28 days, or to the date of the first event, whichever occurs earlier. For a subject who died, the time will be the minimum of dose escalation day, dose reduction day, the day of the last dose + 28 days, or death day.

However, for mortality (death), malignancies (including NMSC), malignancies (excluding NMSC) and MACE related endpoints, all events regardless of their onset within 28 days or beyond after the last dose of tofacitinib will be included. The concept of 28 days is applied to subjects without events that discontinued or completed the study.

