3.5. Safety Endpoints

The safety endpoints in this study include:

- Incidence and severity of adverse events (AEs).
- Incidence and severity of clinical laboratory abnormalities, and change from baseline in clinical laboratory values.
- Incidence of vital sign abnormalities and change from baseline in vital signs.

- Incidence of clinically significant changes in physical examinations from baseline.
- Safety events of interest including adjudicated safety events (eg, opportunistic infections, malignancy, gastrointestinal perforation, hepatic events, and cardiovascular events).

An adverse event is considered treatment emergent relative to a given treatment if the event starts after the first dose. The first dose is defined as the first dose in Study A3921288.

A 3-tier approach will be used to summarize AEs. Under this approach, AEs are classified into 1 of 3 tiers. Different analyses will be performed for different tiers (See [Section 6.6.1](#)).

Tier-1 events: These are pre-specified events of clinical importance and are maintained in a list in the product's Safety Review Plan.

Tier-2 events: These are events that are not tier-1 but are "common". A MedDRA Preferred Term is defined as a tier-2 event if there are at least 4 in any treatment group.

Tier-3 events: These are events that are neither tier-1 nor tier-2 events

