5.2.5. Analysis of Safety Data

Safety data will be summarized based on observed-case data by dose group, regimen group and the subgroup of subjects who are initially assigned to tofacitinib 5 mg BID and later are retreated with tofacitinib 10 mg BID. Missing data will not be imputed.

For dose groups, data collected after the dose escalation from tofacitinib 5 mg BID to 10 mg BID will not be included in the analyses.

For regimen group, data from subjects with dose escalation from tofacitinib 5 mg BID to 10 mg BID will be treated as it is.

For tier-1 adverse events, an unconditional exact method for risk difference proposed by Chan and Zhang (1999)² will be used to compare tofacitinib 10 mg BID to 5 mg BID (dose group), and tofacitinib fixed 10 mg BID to flexible 5 mg/10 mg BID (regimen group). P-values and 95% confidence intervals will be formed. For tier-2 events, the risk difference will be presented along with its 95% confidence interval using the normal approximation for the difference in binomial proportions. For tier-3 events, the risk difference will be reported.

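### SAP 6.6.1 drops the confidence interval for tier-2 adverse events when one group has no events, although SAP 5.2.5 promises it without exception

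*SAP*

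**What the plan says.** SAP 3.5 sorts adverse events into three tiers. Tier 1 is defined thus: "These are pre-specified events of clinical importance and are maintained in a list in the product's Safety Review Plan". Tier 2 covers the remaining common terms: "A MedDRA Preferred Term is defined as a tier-2 event if there are at least 4 in any treatment group". The unit of the 4 is not given; I read it as subjects.

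SAP 5.2.5 sets the methods. Tier 1 uses "an unconditional exact method for risk difference" (Chan and Zhang). For tier 2 it says: "For tier-2 events, the risk difference will be presented along with its 95% confidence interval using the normal approximation for the difference in binomial proportions". It states no exception for zero counts.

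SAP 6.6.1 repeats these methods and adds, for tier 2 only: "In case of zero event rate for tier-2 events in any of group, the 95% confidence intervals will not be computed". It offers no other interval for those rows. The same section calls the tiered analyses exploratory, makes no multiplicity adjustment, and sorts rows within system organ class by descending risk difference. For adverse events of special interest it plans incidence rates: "Confidence intervals (95%) will be computed using the exact Poisson method".

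**The concern.** The two sections disagree on whether every tier-2 row carries an interval. Following 6.6.1 has an odd result. Because a tier-2 term needs at least 4 in one group, a zero in the other group always means 4 or more v 0. For any fixed count in the higher arm, that is the largest imbalance possible. The row loses its interval at that point, while the neighbouring row with a single event in the lower arm keeps one.

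At stake is how the tier-2 table reads. A term seen only on one dose would appear with two proportions and a difference but no measure of uncertainty. SAP 7.1 says that the primary results may go to regulators and be published, so the table may be read by people who cannot recompute it.

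**Working it through.** **Plan's own precision figure.** The documents give no precision figure for adverse events. The only one, in Protocol 9.1, is a half width of about 16% for the Month 6 remission difference with 65 per group and remission rates above 70%. At 70%: 1.96 × √(2 × 0.70 × 0.30 / 65) = 15.75%, which agrees.

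**Inputs.** Safety-set sizes per arm are not given. I assume 65 (half of the planned 130), 69 (half of the 138 enrolled at Amendment 2, under 1:1 allocation) and 70 as a round value.

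**Formulas.** With p = x/n in the higher arm and 0/n in the other:
- Normal approximation (Wald): p ± 1.96 × √(p(1 − p)/n). The zero arm contributes no variance, but the interval can still be computed.
- Newcombe, unstratified: lower limit p − √((p − l₁)² + u₂²), where l₁ is the lower Wilson limit of the higher arm and u₂ = 1.96²/(n + 1.96²) is the upper Wilson limit of the zero arm. The upper limit reduces to u₁, the upper Wilson limit of the higher arm.
- Exact: unconditional interval of Chan and Zhang type, score statistic, grid search over the nuisance parameter.

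**Worked case, 5 v 0 at 70 per arm.** p = 0.0714; Wilson limits for 5/70 are 0.0309 and 0.1566; u₂ = 3.84/73.84 = 0.0520. Lower limit: 0.0714 − √(0.0405² + 0.0520²) = 0.0055, or 0.5 points before rounding up the last digit (0.00548). Upper limit: 15.7 points.

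**Newcombe results** (risk difference in percentage points, 95% interval):

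| Split | 65 per arm | 69 per arm | 70 per arm |
|---|---|---|---|
| 4 v 0 | 6.2 (-0.6 to 14.8) | 5.8 (-0.5 to 14.0) | 5.7 (-0.5 to 13.8) |
| 5 v 0 | 7.7 (0.6 to 16.8) | 7.2 (0.6 to 15.9) | 7.1 (0.5 to 15.7) |
| 6 v 0 | 9.2 (1.8 to 18.7) | 8.7 (1.7 to 17.7) | 8.6 (1.6 to 17.5) |
| 10 v 0 | 15.4 (6.6 to 26.1) | 14.5 (6.2 to 24.7) | 14.3 (6.1 to 24.3) |

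**Comparison of methods at 65 per arm:**

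| Split | Wald | Newcombe | Exact |
|---|---|---|---|
| 4 v 0 | 0.3 to 12.0 | -0.6 to 14.8 | 0.2 to 15.0 |
| 5 v 0 | 1.2 to 14.2 | 0.6 to 16.8 | 1.4 to 17.0 |
| 6 v 0 | 2.2 to 16.3 | 1.8 to 18.7 | 2.6 to 19.3 |

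At 4 v 0 the answer depends on the method: Newcombe includes zero, while Wald and the exact interval just exclude it. The Wald interval is also narrow: 11.7 points, against 14.8 for the exact one.

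**The jump in the rule.** At 65 per arm, 6 v 1 (7.7 points) is printed with a Wald interval of 0.05 to 15.3. The more unbalanced 6 v 0 (9.2 points) is printed with none.

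**How often it could happen.** The chance of a 4-or-more v 0 split in either direction is (1 − p_B)⁶⁵ × P(X_A ≥ 4) + (1 − p_A)⁶⁵ × P(X_B ≥ 4), with binomial counts out of 65. The true rates are my assumptions. The result is 29% for 6% v 1%, 40% for 8% v 1%, 15% for 6% v 2%, and about 3% to 4% for equal rates of 3% to 5%.

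**The case against.** The case for leaving the rule alone has weight. Withholding a normal-approximation interval when a cell is zero is sound practice, and the 4 v 0 row shows why. The analysis is labelled exploratory, SAP 5.1 tests no formal hypotheses, and no planned decision depends on a tier-2 interval. The imbalance is not hidden either: both proportions and the difference are shown, and sorting places the row according to its difference. All of this stands, and it limits the point to a reporting matter. It does not explain why these rows get no replacement when the SAP already specifies two methods that cope with a zero cell: Chan and Zhang for tier 1, and Newcombe (stratified, in 5.2.1) for efficacy.

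Three stronger readings are tempting, and the documents do not support them.
- A reader might infer that the trial's most unbalanced safety signals go without intervals. Tier-1 events keep exact intervals with no zero-event exception, and special-interest events get exact Poisson intervals for their rates.
- A reader might infer that the largest contrasts in the tier-2 table are the ones left bare. Zero is the extreme only for a fixed count in the other arm. At 70 per arm, 12 v 3 is 12.9 points (Wald 2.8 to 22.9) and 20 v 5 is 21.4 points (9.2 to 33.6). Both exceed 6 v 0 at 8.6 points, and both keep their intervals.
- A reader might treat an interval that excludes zero as a positive test. These intervals are unadjusted. At 5 v 0 with 70 per arm, the Newcombe lower limit is 0.5 points, yet Fisher's exact p is 0.058.

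The SAP gives no reason for the exception, so attributing it to a limit of the normal approximation would be a guess.

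**Conclusion.** The point holds as a minor reporting defect confined to tier-2 terms with no events in one group. SAP 5.2.5 and 6.6.1 differ on whether those rows carry an interval, and 6.6.1 leaves them with none. The missing intervals are informative: at an assumed 65 to 70 per arm, the Newcombe interval excludes zero in every split checked from 5 v 0 upward, and includes it at 4 v 0. That pattern is the same at all three arm sizes.

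Safety is part of the primary objective, and one might conclude from this that the trial's main conclusion is at risk. It is not. The Month 6 remission analysis is untouched, and no safety conclusion is formally tied to tier 2.

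**What to change.** In SAP 6.6.1, replace the zero-event exception with wording such as: *when a group has zero events, the 95% CI for the tier-2 risk difference will be computed by the Chan and Zhang exact method*. Put the same statement in SAP 5.2.5. Newcombe would also serve. Because the two can differ at 4 v 0, one should be named before the final analysis. Chan and Zhang has the advantage of already being the tier-1 method.

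Do not simply delete the exception, because the normal-approximation interval would then be printed in the rows where it is least reliable. Tier-2 rows with events in both groups need no change on this account.

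The cost is a little extra programming (the documents show that the methods are specified, not that code exists), a second interval method to footnote in the tier-2 table, and wider intervals in those rows than the normal approximation would give: at 4 v 0 with 65 per arm, 14.8 points against 11.7, about 26% wider. No data collection changes.
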